8.4 Significance level

The significance level for both experiments will be $p \leq 0.05$ (=5%).

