4.1 Primary outcome measures

In the first part of the study (PUK-GHB01), plasma hormone levels, subjective effects assessed by questionnaires, and social cognition parameters assessed by specific computed test batteries, as well as brain activity assessed by electroencephalography (EEG) and functional magnet resonance imaging (fMRI) will serve as primary outcome measures. The results of the neuropsychological test battery performance will serve as longitudinal safety parameters to detect unexpected cognitive impairment after GHB intake. In the second part (PUK-GHB02), plasma hormone levels, GHB levels in plasma, urine, hair, and nails, sleep biomarkers such as brain-derived neurotrophic factor (BDNF), fragile x mental retardation protein (FMRP), IL-beta, IL-6, IL-10, TNF-alpha, CRP, IL-4, IL-18 und IFN-gamma, tryptophan, kynurenin, kynurenic acid, neopterin, malondialdehyd, qinolinsäure, IDO (indolamine-2,3-deoxygenase), substance P, and genetic markers, cognition, memory consolidation assessed by procedural and declarative memory tests, polysomnographic parameters, cerebral GHB-, GABA-, and Glu-concentrations in the ACC, Nacc, and amygdala, resting state connectivity, and measures of daytime sleepiness such as the Epworth Sleepiness

Scale (ESS), as well as subjective mood measures such as the Visual Analog Mood Scale (VAMS), and the Positive and Negative Affect Scale (PANAS) will serve as primary outcome measures.

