6.2 Outcome measures/Flow Chart GHB02

Prescreening		
Time point	Task	Time
	Telefoninterview	
	Zusenden des Fragebogenlinks und der Probandeninformation	
	Persönlichkeitsfragebogen	30-45 min
	Epworth Sleepiness Scale	
	Pittsburgh Sleep Quality Index	
	STAI-X ₂ (Trait)	
	BDI	
	SCL-90	
	MWT-B	
	Fragebogen ausgefüllt?	
	Probandenliste ergänzen	

Screening Night		

Time point	Task	Time
20:00	Empfang	15 min
	Einverständniserklärung	5 min
	Urine drug test	5 min
	Physical Examination	15 min
	Psychiatr. Interview (SKID-I Screening)	10 min
	Alcohol use identification test (AUDIT)	5 min
	Quednow Drug Interview	20 min
22:00	EEG/PSG installation	60 min
	Nail sample 1	
	Saliva_scre	
	Abend-Toilette	20 min
23:00	EEG/PSG connection (IMP)	
23:40	Subject in bed	
23:45	Karolinska Drowsiness Test	5 min
23:50	Waking EEG	10 min
00:00	SLEEP	420 min
08:00	CAR Saliva 1	
08:10	Karolinska Drowsiness Test	5 min
08:15	CAR Saliva 2	
08:15	Morning questionnaire (MQ)	5 min
08:20	Waking EEG	10 min
08:30	CAR Saliva 3	
08:30	EEG/PSG deconnection	10 min
	Morgen-Toilette (ohne Duschen)	10 min
08:45	CAR Saliva 4	
08:50	STAI-X1	5 min
08:55	EWL-60	15 min
09:10	Duschen etc.	
09:30	CAR Saliva 5	
	End of Session	

Adaptation Night 1		
Time point	Task	Time
21:30	Empfang	15 min
21:45	Blood sample 1 (Venflon; EDTA)	10 min
21:55	Drug/Alcohol test	5 min
22:00	EEG/PSG installation	60 min
	Saliva_adap1	
22:00	Light meal (optional)	
	Sweatpatch installation	
	Hair Sample 1	
	Abend-Toilette	
23:15	EEG/PSG connection (IMP)	20 min
23:35	Subject in bed	
23:45	Blood sample 2 (Venflon; EDTA)	2 min

	Karolinska Drowsiness Test	2 min
23:50	Waking EEG	10 min
0:00	SLEEP	420 min
08:00	Blood sample 3 (Venflon; EDTA)	5 min
08:10	Karolinska Drowsiness Test	5 min
08:15	Morning questionnaire (MQ)	5 min
08:20	Waking EEG	10 min
08:30	EEG/PSG deconnection	10 min
	Morgen-Toilette/Urine sample 1	10 min
8:40	Random Number Generation Task (RNG)	10 min
8:50	Psychomotor Vigilance Task incl. SSS	10 min
9:00	STAI-X1	5 min
9:05	EWL-60	15 min
9:20	Duschen etc.	
	End of Session	

Experimental Night 1		
Time point	Task	Time
19:30	Empfang	15 min
20:00	Blood sample 1 (Venflon; 2 EDTA; Protein, Kalium-Fluorid, Heparin-Plasma, 2 PAX)	15 min
20:40	Drug/Alcohol test	5 min
20:45	EEG/PSG installation	60 min
	Saliva_exp1	
	Light meal (optional)	
	Sweatpatch installation	
21:45	STAI-X1, PANAS, EWL-60, EQ, VAMS	20 min
22:05	Paired Word List Task 1	40 min
22:45	Walker 1	10 min
	Abend-Toilette	
23:10	EEG/PSG connection	20 min
	Subject in bed	

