23:30	*** GHB or Placebo ***	5 min
23:47	Karolinska Drowsiness Test	2 min
23:50	Waking EEG	10 min
23:55	Blood sample 2 (Venflon; 2 EDTA, Protein, Kalium-Fluorid, Heparin-Plasma, 2 PAX)	5 min
00:00	SLEEP	420 min
08:00	CAR Saliva 1	
	Blood sample 3 (Venflon; 2 EDTA, Protein, Kalium-Fluorid, Heparin-Plasma, 2 PAX)	10 min
08:10	Karolinska Drowsiness Test	5 min
08:15	CAR Saliva 2	
	Morning questionnaire (MQ)	5 min
08:20	Waking EEG	10 min
08:30	CAR Saliva 3	
	EEG/PSG deconnection	10 min

08:40	Morgen-Toilette/Urine sample 2	10 min
08:45	CAR Saliva 4	
08:50	Paired Word List Task 2	40 min
09:30	CAR Saliva 5	
09:35	Walker 2	10 min
09:45	IOWA Gambling Task (IGT)	20 min
10:05	Random Number Generation Task (RNG)	10 min
10:15	Psychomotor Vigilance Task incl. SSS	10 min
10:25	Delay discounting task	5 min
10:30	STAI-X1, PANAS, EWL-60, EQ, VAMS	20 min
10:50	Duschen etc.	
	End of Session	

Post Acute Measurement 1		
Time point	Task	Time
12:00 (t12h)	PANAS, EWL-60, VAMS	
16:00 (t16h)	PANAS, EWL-60, VAMS	
19:45	Empfang	
20:00 (t24h)	PANAS, EWL-60, VAMS	
	Blood sample 4 (Venflon; 2 EDTA, Protein, Kalium-Fluorid, Heparin-Plasma, 2 PAX)	
	Nail sample 2	

Adaptation Night 2		
Time point	Task	Time
21:30	Empfang	15 min
21:45	Blood sample 1 (Venflon; EDTA)	10 min
21:55	Drug/Alcohol test	5 min
22:00	EEG/PSG installation	60 min
	Saliva_adap2	
22:00	Light meal (optional)	
	Sweatpatch installation	
	Hair Sample 1	
	Abend-Toilette	
23:15	EEG/PSG connection (IMP)	20 min
23:35	Subject in bed	
23:45	Blood sample 2 (Venflon; EDTA)	2 min
	Karolinska Drowsiness Test	2 min
23:50	Waking EEG	10 min
0:00	SLEEP	420 min
08:00	Blood sample 3 (Venflon; EDTA)	5 min
08:10	Karolinska Drowsiness Test	5 min
08:15	Morning questionnaire (MQ)	5 min
08:20	Waking EEG	10 min
08:30	EEG/PSG deconnection	10 min

	Morgen-Toilette/Urine sample 1	10 min
8:40	Random Number Generation Task (RNG)	10 min
8:50	Psychomotor Vigilance Task incl. SSS	10 min
9:00	STAI-X1	5 min
9:05	EWL-60	15 min
9:20	Duschen etc.	
	End of Session	

Experimental Night 2		
Time point	Task	Time
19:30	Empfang	15 min
20:00	Blood sample 1 (Venflon; 2 EDTA, Protein, Kalium-Fluorid, Heparin-Plasma, 2 PAX)	15 min
20:40	Drug/Alcohol test	5 min
20:45	EEG/PSG installation	60 min
	Saliva_exp2	
	Light meal (optional)	
	Sweatpatch installation	
21:45	STAI-X1, PANAS, EWL-60, EQ, VAMS	20 min
22:05	Paired Word List Task 1	40 min
22:45	Walker 1	10 min
	Abend-Toilette	
23:10	EEG/PSG connection	20 min
	Subject in bed	
23:30	*** GHB or Placebo ***	5 min

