23:47	Karolinska Drowsiness Test	2 min
23:50	Waking EEG	10 min
23:55	Blood sample 2 (Venflon; 2 EDTA, Protein, Kalium-Fluorid, Heparin-Plasma, 2 PAX)	5 min
00:00	SLEEP	420 min
08:00	CAR Saliva 1	
	Blood sample 3 (Venflon; 2 EDTA, Protein, Kalium-Fluorid, Heparin-Plasma, 2 PAX)	10 min
08:10	Karolinska Drowsiness Test	5 min
08:15	CAR Saliva 2	
	Morning questionnaire (MQ)	5 min
08:20	Waking EEG	10 min
08:30	CAR Saliva 3	
	EEG/PSG deconnection	10 min
08:40	Urine sample 2	10 min
08:45	CAR Saliva 4	
08:50	Paired Word List Task 2	40 min
09:30	CAR Saliva 5	
09:35	Walker 2	10 min
09:45	IOWA Gambling Task (IGT)	20 min
10:05	Random Number Generation Task (RNG)	10 min
10:15	Psychomotor Vigilance Task incl. SSS	10 min

10:25	Delay discounting task	5 min
10:30	STAI-X1, PANAS, EWL-60, EQ, VAMS	20 min
10:50	Duschen etc.	
	End of Session	

Post Acute Measurement 2		
Time point	Task	Time
12:00 (t12h)	PANAS, EWL-60, VAMS	
16:00 (t16h)	PANAS, EWL-60, VAMS	
19:45	Empfang	
20:00 (t24h)	PANAS, EWL-60, VAMS	
	Blood sample 4 (Venflon; 2 EDTA, Protein, Kalium-Fluorid, Heparin-Plasma, 2 PAX)	
	Nail sample 2	

Time point	Sample	Time
Screening night	Nail sample 1	
Adapt night 1	Hair sample 1	
Post akut 1	Nail sample 2	
Adapt night 2	Hair sample 2	
Post akut 2	Nail sample 3	
2 days post EN 2	Hair sample 3	
2 weeks post EN 2	Nail sample 4 (at home)	
3 weeks post EN 2	Nail sample 5 (at home)	
4 weeks post EN 2	Nail sample 6 (at home)	
5 weeks post EN 2	Hair sample 4	
	Nail sample 7	
6 weeks post EN 2	Nail sample 8 (at home)	
7 weeks post	Nail sample 9 (at home)	

EN 2		
8 weeks post EN 2	Nail sample 10 (at home)	
9 weeks post EN 2	Nail sample 11 (at home)	
10 weeks post EN 2	Nail sample 12 (at home)	
11 weeks post EN 2	Nail sample 13 (at home)	
12 weeks post EN 2	Nail sample 14 (at home)	
13 weeks post EN 2	Nail sample 15 (at home)	
14 weeks post EN 2	Nail sample 16 (at home)	

Experimental night 3		
Zeit (geplant)	Task	Time
21:15	Empfang	
21:30	Drug/Alcohol test	
21:55	Blood sugar measurement	
22:00	Light meal (optional)	
22:15	MR-Fragebogen, VAS, PANAS, VAMS, EQ	
22:20	EEG/PSG installation	
	Sweatpatch 5	
23:00	MRI Baseline	
	Anatomisches MRI	
	MRS	
	Resting Sate fMRI	
23:30	***GHB or Placebo***	
00:00	Blood Sample 1 (Butterfly; 2 EDTA)	
00:05	MRI Session 1	
	Anatomisches MRI	
	MRS NAcc, ACC, Amygdala	
	Resting Sate fMRI	
01:40	Blood Sample 2 (Butterfly; 2 EDTA)	
01:45	VAS, PANAS, VAMS	
	Abend Toilette	
	EEG/PSG connection	
01:50	Karolinska Drowsiness Test	

02:00	Waking EEG	
	Sleep	

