8.1 Primary and secondary endpoints

The primary endpoint of PUK-GHB01/02 is the detection of alterations in brain activity, GHB-, GABA-, and Glu-concentrations, and blood parameters after the administration of GHB. The secondary endpoint of trial I is the correlation between serum hormone levels and neurocognitive as well as subjective measures. The secondary endpoint of trial II is the correlation of blood parameters with cognitive alterations as well as subjective measures and the correlation of cerebral GHB-, GABA-, and Glu-concentrations with results of the other experiments GHB01 and GHB02.

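### Sections 4.1 and 8.1 name different primary sets and test them at an unadjusted 5%, so the chance of a false-positive primary exceeds 5% on either list

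*Combined protocol and SAP*

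**What the plan says.** Section 4.1 sets out the primary outcomes by experiment. For PUK-GHB01 it begins "In the first part of the study (PUK-GHB01), plasma hormone levels, subjective effects assessed by questionnaires, and social cognition parameters" and adds EEG and fMRI. The neuropsychological battery is given a different role there, as a safety parameter. For PUK-GHB02 the list covers hormones, GHB levels, some 18 named biomarkers, genetic markers, cognition, memory, polysomnography, cerebral concentrations in three regions, resting-state connectivity, sleepiness and mood. It ends "and the Positive and Negative Affect Scale (PANAS) will serve as primary outcome measures".

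Section 8.1 gives another definition for both experiments: "The primary endpoint of PUK-GHB01/02 is the detection of alterations in brain activity, GHB-, GABA-, and Glu-concentrations, and blood parameters" after GHB. Cognitive and subjective measures appear there only inside secondary correlations. Social cognition and memory are not named as primary.

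Section 8.2 derives at least 19 subjects per experiment from d = 0.7, two-tailed 5% and 80% power. Section 8.3 uses one ANOVA approach for all dependent variables. Section 8.4 reads "The significance level for both experiments will be" p ≤ 0.05. No section states how several primary results combine.

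On sleepiness, 4.1 names "measures of daytime sleepiness such as the Epworth Sleepiness" Scale (ESS). Section 4.2.2 lists ESS among the assessments made after GHB. The flow chart in 6.2 shows "Epworth Sleepiness Scale" only under prescreening.

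**The concern.** A 5% level limits the false-positive risk of an experiment only if one test decides it, or if a rule ties several tests together. Here many outcomes carry the primary label, each is tested at 5%, and no such rule is given. If GHB had no effect on any of them, the chance that at least one came out significant would be above 5%.

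The two definitions add a second problem. Because 4.1 and 8.1 disagree and the sample size points to no single variable, the primary result could be chosen after the data are seen and still agree with one section of the protocol.

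**Working it through.** **1. The plan's own sample size.** The design is a crossover, so the test is paired, with d = 0.7 read as the standardised within-subject difference. Power comes from the noncentral t distribution with n − 1 degrees of freedom and noncentrality d√n, two-sided 5%.
- n = 18: 0.7 × √18 = 2.97, power 79.9%.
- n = 19: 0.7 × √19 = 3.05, power 82.3%.

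So 19 is reproduced, for one test. At the planned sizes (32 and 20) one test has 97.0% and 84.4% power. Within one PUK-GHB01 dose group of 16 it has 74.5%.

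**2. Counting tests.** The documents give no count. I take one test per named outcome that could show a drug effect. I leave out GHB levels (not a plausible null), genetic markers, ESS and memory tasks that the flow chart does not schedule.
- PUK-GHB01 under 4.1: 8 hormones + 4 questionnaires + 4 social cognition tests + fMRI = 17 (18 with EEG, which Table 4 does not schedule).
- PUK-GHB01 under 8.1: section 4.2.1 lists 16 non-GHB blood analytes; 16 + fMRI = 17. If only the 8 hormones count as blood parameters, 8 + 1 = 9.
- PUK-GHB02 under 4.1: 3 hormones + 18 markers + 4 cognitive + 2 memory + polysomnography + 6 spectroscopy (GABA and Glu in 3 regions) + connectivity + VAMS + PANAS = 37.
- PUK-GHB02 under 8.1: 21 blood markers + 6 spectroscopy + connectivity = 28.
- Most lenient reading of 8.1: one test per domain. This gives 3 tests, or 2 in PUK-GHB01, where no spectroscopy is planned.

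**3. Chance of at least one false positive.** For k independent tests it is 1 − 0.95^k. For correlated tests I use k normal statistics with a common correlation, integrated numerically. The documents give no correlations, so a range is shown.

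| Tests | 0 | 0.5 | 0.8 | 0.95 |
|---|---|---|---|---|
| 2 | 9.8% | 9.1% | 7.8% | 6.5% |
| 3 | 14.3% | 12.5% | 9.8% | 7.3% |
| 9 | 37% | 26.9% | 16.5% | 9.8% |
| 17 | 58% | 38.6% | 21.2% | 11.3% |
| 28 | 76% | 49.1% | 25.1% | 12.4% |
| 37 | 85% | 55.4% | 27.3% | 13.0% |

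Simulated paired t-tests with 20 men and 37 outcomes gave slightly more: 57.6%, 28.5% and 13.5% at correlations 0.5, 0.8 and 0.95. Every cell exceeds 5%.

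**4. Cost of adjusting instead of selecting.** Bonferroni (0.05/k) in the same paired test at d = 0.7:
- PUK-GHB01, 4 domains from 4.1: level 0.0125, power 89.6% at 32 men (26 needed for 80%).
- PUK-GHB02, 3 domains from 8.1: level 0.0167, power 69.1% at 20 men (25 needed for 80%).

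**5. ESS.** The only scheduled ESS comes before any dose, so it cannot differ between GHB and placebo within a man. The flow chart does schedule a "Karolinska Drowsiness Test" after dosing on each experimental night. Section 4.2.2 calls the Karolinska measure a Sleepiness Scale instead.

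**The case against.** The strongest defence is that this is a mechanistic study in healthy volunteers, with GHB as a model substance, and that strict error control suits confirmatory trials. Some of that stands: calling most outcomes exploratory would remove much of the problem. But the protocol calls them primary, powers a hypothesis test in 8.2 and predicts significant alterations in 3.3.

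Section 8.4 could be read as 5% per experiment. No procedure is given to achieve that, so it operates per test. It is fair that 8.1 does separate primary from secondary endpoints; the gap lies within the primary set. It is also fair that 8.2 draws its effect sizes from neuroendocrine and cognitive parameters, so a field is indicated. No variable is named, however, and 8.1 uses cognitive measures only in secondary correlations.

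A reader might infer several stronger things that the documents do not support:
- **That 4.1 makes every listed outcome primary.** It does not; the neuropsychological battery is a safety parameter.
- **That the error rate is 85%, or any particular figure.** That value needs 37 independent true nulls. Related analytes in the same men are unlikely to be independent, and section 3.1.1 reports earlier GHB effects on cortisol, ACTH and subjective state.
- **That 8.1 is clearly the shorter list in PUK-GHB01.** Read plainly, blood parameters give 17 tests, as many as under 4.1.
- **That the sample size is wrong.** It is correct for a single paired test.
- **That "Psychomotor Vigilance Task incl. SSS" supplies a replacement sleepiness rating.** The documents never expand SSS. The ESS mismatch is also a scheduling conflict and does not contribute to the error rate.

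**Conclusion.** The concern holds. The primary question is not uniquely defined, and on either definition the stated level does not hold the chance of a false-positive primary at 5%. This rests on one assumption about use: that any one significant primary counts as a positive result. The plan neither says so nor excludes it. The firm finding is the direction, since even two tests correlated at 0.95 give 6.5%. The larger figures illustrate scale under assumed counts and correlations. Section 8.2 makes no allowance for multiplicity, and this matters more in PUK-GHB02, with 20 men, than in PUK-GHB01, with 32. The power figures assume d = 0.7 for whichever contrast is chosen. The contradiction should be removed before any analysis.

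**What to change.** Make 4.1 and 8.1 name the same primary outcome for each experiment, chosen by the sponsor and defined by measure, time point or summary, and contrast. Test it at two-sided 5% and tie it to 8.2.

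If several primaries are kept, state an adjustment such as Holm or Bonferroni and restate power. This looks affordable in PUK-GHB01 but leaves PUK-GHB02 short of 80% with three domains.

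If the PUK-GHB01 primary comes from sessions 1 and 2, state how the two dose groups enter the contrast. Power is 97% for all 32 men if d = 0.7 holds for the pooled contrast, and 74.5% within one group of 16. Sessions 3 and 4 have no dose split.

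Label the remaining outcomes secondary or exploratory, with false discovery rate control for those used to support claims.

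Reconcile ESS across 4.1, 4.2.2 and 6.2. Either drop it as a primary drug-effect measure or use a sleepiness measure already scheduled after dosing, such as the Karolinska entry, with its name aligned between 4.2.2 and 6.2.

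The cost is wording, plus communication of the protocol change to Swissmedic and the ethical commission under section 10.2. Fewer outcomes can be called primary, and some p-values near 0.05 will no longer count.

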8.5 Drop outs

Drop outs will be excluded from the study.

9 Study specific precautions and obligations

9.1 Specific precautions.

For the study participants it is not allowed to use any illegal drugs during or seven days prior to the experiments. Participants should abstain from alcohol at least 48 h hours. Furthermore, it is not allowed to drive motor vehicles or to use machines subsequent to the experiments.

10 Investigators obligation

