
All experiments are monitored by a medical doctor. In case of any unexpected incidence threatening the subject's health or if the subject wishes to abandon the study, the procedure will be stopped immediately. All participants will provide urine for a drug screening to control for current drug use. Any drug use pattern will be assessed using the Interview for Psychotropic Drug Consumption (Quednow et al., 2004). The subjects will receive 225 CHF for participating in the first to experimental days and the pre- and post-tests. An additional amount of 75 CHF can be earned through the neuroeconomical tests. The participation in the two fMRI sessions will be compensated with additional 100 CHF.

[figure not shown]

Chart 1 Order of study sessions

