4.2.2 PUK-GHB02: sleep and memory

Following screening procedures prior to enrollment into the experiment, 20 male healthy subjects will be assessed with an actiwatch (for two weeks), questionnaires (Eigenschaftswörterliste [EWL-60], Epworth Sleepiness Scale [ESS], Alcohol Use Identification test [AUDIT], Pittsburgh Sleep Quality Index, Morning Questionnaire [MQ], Positive and Negative Affect Schedule [PANAS], Visual Analog Mood Scale [VAMS], Evening Questionnaire [EQ], Karolinska Sleepiness Scale [KSS], Beck Depression Inventory [BDI], Persönlichkeitsfragebogen, State-Trait Anxiety Inventory [STAI], Mehrfach-Wortschatz-Intelligenztest [MWT-B], Symptomcheckliste 90 [SCL-90]), cognitive tests (Random Number Generation Task [RNG], IOWA Gambling Task [IGT], Psychomotor Vigilance Task [PVT], Delay Discounting Task [DDT]), tests of procedural and declarative memory consolidation (Learning of Texts Task [LTT], Two-Dimensional Object-Location Memory Task [2D-OLMT], Walker Finger Sequence-Tapping Task [FS TT], Paired Associate Word List [PÄWL]), polysomnography (electroencephalography [EEG], electromyography [EMG] and pulse oxymetry), magnetic resonance spectroscopy with electroencephalography (MRS/EEG), functional magnetic resonance imaging with electroencephalography (fMRI-EEG), saliva cortisol, and blood tests (IL-beta, IL-6, IL-10, TNF-alpha, CRP, IL-4, IL-18 und IFN-gamma, tryptophan, kynurenin, kynureninic acid, neopterin, malondialdehyd, qinolinsäure,IDO (indolamine-2,3-deoxygenase), substance P, cortisol, progesterone, BDNF, FMRP, genetic markers, prolaktin) after two applications of GHB (50 mg/kg p.o. vs. placebo – cross over design). Each subject will pass through 7 study nights: one screening night, two adaptation nights and four experimental nights (GHB vs. placebo) (see chart 1). The screening night will take place before the first experimental session. The two first experimental nights will be preceded by one adaptation night. The experimental nights 1+2 will take place in the sleep laboratory of the University of Zurich in collaboration with [name]. The experimental nights 3+4 will take place in the magnetic resonance imaging center (MRZ) of the Psychiatric Hospital of the University of Zurich. The assessment will follow the Good Clinical Practice (GCP) guidelines. Memory testing consists of two steps. First, learning tasks are performed prior to sleep. Second, recalling tasks are performed one hour after awakening. Blood tests for neuroendocrinologic, pharmacokinetic, and depression and sleep biomarker measures will be taken 18 times in total (adaptation nights 6x, experimental nights 6x, post-experimental-night evenings 2x, MRS-fMRI/EEG-nights 4x). Further pharmacokinetic samples will be taken as follows: five hair samples (T0: before testing, T1: days post-experimental night I, T2: seven days post-experimental night I, T3: two days post-experimental night II, T4: six weeks post-experimental night I, T5: before experimental night III, T6: the day after experimental night

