4.5 Blood and other biosamples

4.5.1 Procedure

Experiment I: Every study subject takes part in at least two experimental sessions (GHB vs. placebo). An amount of blood of 150 ml (6 samples) will be taken by the principal investigator through an intravenous catheter during each session. For both sessions, a total amount of blood of 300 ml will be taken.

Experiment II: Every study subject takes part in four experimental sessions (2 x GHB vs. placebo), plus one preceding screening-night and one adaptation night anterior to each experimental night. A total amount of blood of 250 ml (18 samples, see 6.2) will be taken by a medical professional or a study nurse through an intravenous catheter during each session. Each sample will be tested for the quantities of the plasma markers IL-beta, IL-6, IL-10, TNF-alpha, CRP, IL-4, IL-18 und IFN-gamma, tryptophan, kynurenin, kynureninic

acid, neopterin, malondialdehyd, qinolinsäure, IDO (indolamine-2,3-deoxygenase) and substance P cortisol, progesterone, GHB, BDNF, FMRP, genetic markers, and prolactin. Moreover, other biosamples will be taken as follows: five hair samples (T0: before testing, T1: 2 days post-experimental night I, T2: seven days post-experimental night I, T3: two days post-experimental night II, T4: six weeks post-experimental night I, T5: before experimental night III, T6: the day after experimental night III, T7: the day after experimental night III), seven sweat samples (one sweat patch per night), four urine samples (after every adaptation and experimental night), nine nail samples (weekly nail clipping).

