8.2 Number of subjects

Comparable studies to the effects of GHB and other challenges on neuroendocrine and cognitive parameters in awake and sleeping subjects (Carter et al., 2009a, Dumont et al., 2009, Grove-White and Kelman, 1971, Marshall et al., 2006) revealed effect sizes of $d=0.7-1.2$. With a conservative assumption of $d=0.7$, an α -error probability of 5%, and a power of 80% (two-tailed), we would need at least 19 subjects to detect significant differences in each experiment.

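### Section 8.5 does not say whether a drop-out's data are kept; read as a data exclusion, it discards GHB/placebo pairs already completed in GHB02, which plans 20 men against a minimum of 19

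*Combined protocol and SAP*

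**What the plan says.** Section 8.5 consists of one sentence: "Drop outs will be excluded from the study". Sections 4.2.1 and 4.2.2 add that the procedure stops if a subject wishes to abandon the study; they do not mention his data. Section 8.3 specifies repeated-measures ANOVA for every dependent variable, with no missing-data rule.

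For GHB02, section 4.5.1 states "Every study subject takes part in four experimental sessions (2 x GHB vs. placebo", and section 4.7.2 gives each of the 20 men GHB on two occasions and placebo on two. Section 2.2.2 assigns sleep architecture, biomarkers, cognition and memory to sessions 1 and 2, and MRS and resting-state fMRI/EEG to sessions 3 and 4. Both sets compare the same dose with placebo. The venues differ too: "The experimental nights 1+2 will take place in the sleep laboratory of the University of Zurich", while nights 3 and 4 are at the MR centre.

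For GHB01, section 4.5.1 says "Every study subject takes part in at least two experimental sessions (GHB vs. placebo", and section 4.2.1 pays for the scans separately: "The participation in the two fMRI sessions will be compensated with additional 100 CHF".

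On sample size, section 8.2 states "we would need at least 19 subjects to detect significant differences in each experiment". It adds no allowance for drop-out.

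**The concern.** A man who leaves before his last planned session is a drop-out in the ordinary sense. In GHB02 there are four planned sessions, so this includes a man who attends nights 1 and 2 and then does not return for the MR nights. There is probably time for this to happen: hair sampling is listed as "T4: six weeks post-experimental night I, T5: before experimental night III", so if those labels run in time order, at least six weeks separate night I from night III.

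If 8.5 removes all his data, it removes a complete within-subject pair from comparisons that need nothing from nights 3 and 4. Two things are at stake. First, usable pairs are lost in an experiment with one man to spare. Second, because the rule can be read in two ways, the analysis set could be chosen after results are known. Restricting the analysis to completers might also select men, if leaving is related to how they responded to GHB.

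**Working it through.** **1. Is the nights 1+2 pair complete for a man who leaves after night 2?**

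- Treatment: that nights 1+2 hold one GHB and one placebo night follows from 2.2.2 read with 4.5.1 and 4.7.2. The randomisation text does not state this within-pair restriction separately, so it is a well-supported inference.
- Memory: in the section 6.2 flow charts, the paired word list and finger-tapping tasks appear only in experimental nights 1 and 2, with morning recall ("Paired Word List Task 2") in each. Nights 3 and 4 contain neither task. The memory pair is complete.
- Sleep: the overnight recordings of nights 1 and 2 are complete.
- Blood and post-acute mood: complete only if he also attended Post Acute Measurement 2, which has mood scales at 12:00, 16:00 and 20:00 and blood sample 4 at 20:00 on the day after night 2.
- Hair and nails: sampling continues for weeks after night 2, so later samples would be missing.

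**2. Reproducing the plan's 19**

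Inputs from 8.2: d = 0.7, two-sided alpha 5%, power 80%. Take d as the mean paired difference divided by its SD. With c = t(0.975, n−1) and noncentrality d√n:

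power = P(T > c) + P(T < −c), where T is noncentral t on n−1 degrees of freedom.

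For n = 19 the noncentrality is 0.7 × √19 = 3.05 and power is 82.3%. For n = 18 it is 79.9%. The smallest n with at least 80% is 19, as stated.

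**3. Cost of removing completed pairs**

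Start from 20 men and remove k men who left after night 2. The CI half-width is t(0.975, n−1)/√n, in SDs of the paired difference.

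| k removed | n | power | change from 84.4% | 95% CI half-width |
|---|---|---|---|---|
| 0 (pairs kept) | 20 | 84.4% | – | 0.468 SD |
| 1 | 19 | 82.3% | −2.1 points | 0.482 SD |
| 2 | 18 | 79.9% | −4.4 points | 0.497 SD |
| 3 | 17 | 77.3% | −7.0 points | 0.514 SD |
| 4 | 16 | 74.5% | −9.9 points | 0.533 SD |

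The margin is 20 − 19 = 1 man. With two removed, power is 0.1 points below the 80% target; with three, 2.7 points below.

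**4. How likely is that?**

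The documents give no drop-out rate. Assume each of 20 men independently leaves after night 2 with probability q. The chance of falling below 19 is 1 − (1−q)^20 − 20q(1−q)^19.

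| q (assumed) | fewer than 19 men | three or more lost | average power |
|---|---|---|---|
| 5% | 26% | 7.5% | 82.1% |
| 10% | 61% | 32% | 79.7% |
| 15% | 82% | 60% | 77.0% |
| 20% | 93% | 79% | 74.0% |

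**5. Selection, illustration only**

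If the mean GHB effect in leavers differs from that in stayers by Δ, the completer mean shifts by (k/20) × Δ. For an assumed Δ of 0.5 to 1.0 SD, that is 0.05 to 0.10 SD with k = 2 and 0.10 to 0.20 SD with k = 4. Nothing in the documents supports a value or a sign for Δ.

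**The case against.** The sentence says excluded from the study, not from the analysis. Ending participation is an equally natural meaning, and it fits 4.2.1 and 4.2.2, which describe withdrawal as stopping the procedure. The consent pages are not in the available text and might address data already collected. This stands: a reader might infer that the plan definitely deletes these data, and the documents do not establish that. What supports the other reading is that the sentence is placed under Statistics, where it is the only rule on drop-outs.

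The power loss is small at first. One loss leaves exactly 19 men and two leave 79.9%. The high probabilities in step 4 rest on assumed rates, place all attrition after night 2, and count the crossing of a threshold where power falls only from 82.3% to 79.9%. This also stands. A reader might infer that GHB02 is seriously underpowered because of 8.5; the figures do not show that.

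A simple split into sessions 1+2 and sessions 3+4 would not suit every outcome. PANAS and VAMS are collected on all four nights. Section 8.1 plans to correlate cerebral concentrations with other results, and within GHB02 a correlation with nights 1+2 data needs men who have both pairs. The remedy must therefore work outcome by outcome.

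**Conclusion.** The point holds as an undefined rule with an avoidable consequence, and it should be fixed. Section 8.5 neither defines a drop-out nor says whether his data are kept. If it is applied as a data exclusion, completed GHB02 memory and sleep pairs are discarded for no analytical reason, at a cost of 2.1, 4.4, 7.0 or 9.9 points of power for 1, 2, 3 or 4 men. That is modest, and material from the third man. The result rests on d = 0.7 being the standardised paired difference, which reproduces 8.2, and on nights 1+2 being one GHB/placebo pair.

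Three stronger inferences are not supported:

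- That everything attached to nights 1+2 is complete for such a man. Blood sample 4, the post-acute mood scales, and the later hair and nail samples come after night 2.
- That completer analysis biases the results by a known amount. Selection is possible, but its size and direction are not given. Keeping completed pairs removes it only for men who leave after a pair is complete.
- That GHB01 is affected in the same way. The wording of 4.5.1 and the separate scan payment suggest that its first two sessions stand alone, and it plans 32 men; 8.5 simply does not say so.

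**What to change.** Replace 8.5 with:

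> A drop-out is a man who ends participation before his last planned session. Data collected up to that point are kept. Each outcome is analysed in every man who completed the GHB/placebo pair(s) that the outcome requires, whether or not he completed the other sessions; an analysis restricted to men who completed all planned sessions is a sensitivity analysis. Outcomes measured in all four sessions, and correlations between sessions 1+2 and sessions 3+4, use men with the data needed for that analysis, and the number of men is reported for each. Withdrawals are reported with reasons by treatment, and adverse events for every dosed man.

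Add to 8.2:

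> The stated 80% power in GHB02 holds only if at least 19 men complete the relevant GHB/placebo pair.

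State in 4.5.1 whether a GHB01 man has two or four planned sessions, so that the definition works there too. The repeated-measures ANOVA of 8.3 stays as it is.

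The cost is wording only: no extra men, visits or drug. The downside is that the number of men differs between outcomes. Men who leave before their second condition still contribute nothing to that comparison.
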